8.1.1 Laboratory Assessments of Clinical Activity

Samples for the following laboratory assessments of clinical activity and hormone levels will be sent to the study site local laboratory for analysis:

Table 3: Laboratory Tests Sent to the Study Site Local Laboratory for Analysis of Disease-related Endpoints

Profile	Laboratory Test
Clinical activity	PSA
Hormone levels	testosterone

PSA = prostate-specific antigen

8.2 SAFETY ASSESSMENTS

Safety assessments will consist of monitoring and recording AEs, including SAEs and AESIs, performing protocol-specified safety laboratory assessments, measuring protocol-specified vital signs, and conducting other protocol-specified tests that are deemed critical to the safety evaluation of the study. Planned timing for all safety assessments is provided in the SOA ([Section 1.3](#)).

Certain types of events require immediate reporting to the Sponsor, as described in [Section 8.3.1.1](#).

8.2.1 Medical History and Demographic Data

Medical history, including clinically significant diseases, surgeries, cancer history (including stage, date of diagnoses, and prior cancer therapies and procedures), reproductive status, smoking history, use of alcohol, and drugs of abuse, will be recorded at baseline. In addition, all medications (eg, prescription drugs, OTC drugs, vaccines, herbal or homeopathic remedies, nutritional supplements) used by the participant within 28 days prior to the first dose of study intervention will be recorded. Demographic data may include age, sex, and race/ethnicity.

8.2.2 Physical Examinations

A complete physical examination should be performed at screening and should include an evaluation of the head, eyes, ears, nose, and throat, and the cardiovascular, dermatological, musculoskeletal, respiratory, gastrointestinal, genitourinary, and neurological systems. Any abnormality identified at baseline should be recorded on the Medical History eCRF page.

Eastern Cooperative Oncology Group (ECOG) performance status (see [Appendix 2](#)) should be assessed per the SOA in [Section 1.3](#).

At subsequent visits (or as clinically indicated), limited, symptom-directed physical examinations should be performed. Changes from baseline abnormalities should be recorded in participant notes. New or worsened clinically significant abnormalities should be recorded as AEs on the Adverse Event eCRF page.

8.2.3 Vital Signs

Vital signs should include measurements of respiratory rate, pulse rate, systolic and diastolic blood pressure, pulse oximetry (required only at screening), and temperature as outlined in the SOA ([Section 1.3](#)). Vital signs collected at the screening visit should be recorded on the eCRF. For each visit thereafter, only vital signs obtained prior to the study intervention administration as outlined in the SOA or during an AE (eg, temperature or event of fever) should be recorded on the eCRF. All vital signs collected per protocol should be documented in the participant's medical record.

Vital signs should be measured within 15 minutes prior to and after the administration of study intervention. Vital signs may be measured, if medically indicated, at other time points.

8.2.4 Electrocardiograms

A single electrocardiogram (ECG) recording will be obtained at baseline, as outlined in the SOA ([Section 1.3](#)) and may be obtained at unscheduled time points as indicated.

All ECG recordings must be performed using an institutionally-approved ECG. Lead placement should be as consistent as possible. ECG recordings should be performed after the participant has been resting in a supine position for at least 10 minutes.

For safety monitoring purposes, the Investigator must review, sign, and date all ECG tracings. ECG tracings will be kept as part of the participant's medical record. The Investigator's assessment (ie, normal, abnormal [not clinically significant], or abnormal [clinically significant]) should be recorded on the appropriate eCRF page. Any morphologic waveform changes or other ECG abnormalities should be documented on the eCRF page.

8.2.5 Clinical Safety Laboratory Assessments

Clinical laboratory tests will be performed at the local institution as described in the SOA ([Section 1.3](#)).

The Investigator must review the laboratory report, document this review, and designate results as being not clinically significant or clinically significant. Clinically significant abnormal findings are those for which an action was taken (ie, providing fluid, transfusion, medication, and/or holding, delaying, or discontinuing study intervention) or those that are not associated with the underlying disease, unless judged by the Investigator to be more severe than expected for the participant's condition. Clinically significant changes occurring during the study should be documented on the appropriate eCRF. The laboratory reports must be filed with the source documents.

In the event of a Grade 3 or Grade 4 laboratory toxicity, the test for the abnormal laboratory value should be repeated until the event is resolved to \leq Grade 1 or baseline.

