3 OBJECTIVES AND ENDPOINTS

The study objectives and endpoints are listed in [Table 2](#).

Table 2: Objectives and Corresponding Endpoints

Objectives	Endpoints
Primary	

 To determine the safety of each immunotherapy combination in participants with mCRPC. 	
 Incidence and severity of AEs.
Secondary	
 ORR: A composite endpoint where response is defined as a participant meeting at least one of the following: 
 CTC response: Change from unfavorable (≥ 5 cells/7.5 mL of blood) to favorable (≤ 4 cells/7.5 mL of blood). Participants with a baseline CTC value < 5 cells/7.5 mL of blood will not be evaluated for this criterion. PSA response: Confirmed PSA response is defined as $\geq 50\%$ reduction in PSA from baseline, with a repeat assessment confirming the result at least 3 weeks later. Participants without a baseline and at least 2 post-baseline PSA assessments will not be evaluated for this criterion. Confirmed response of CR or PR by objective radiographic disease assessment using modified RECIST version 1.1 (ie, CR or PR and no progression in bone per the PCWG3; Scher et al., 2016). Per RECIST, to be assigned a best overall response of CR or PR, changes in tumor measurements must be confirmed by repeat assessments that should be performed no less than 4 weeks after the criteria for response are first met. Participants who received at least 1 dose of the combination study intervention or component

	
of the combination but do not have RECIST assessment for any reason will be counted as not responding.
 
 • DCR at 9 months: Defined as CR, PR, or SD for 9 months as best response by PCWG3-modified RECIST 1.1. Participants who received at least 1 dose of the study intervention combination or component of the combination but do not have RECIST assessment for any reason will be counted as not responding. • rPFS: Defined as time from initiation of study intervention to the first objective evidence of radiographic progression, or death due to any cause (whichever occurs first). • OS: Defined as the time from initiation of study intervention until death due to any cause. • OS rate at 12 months.

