10.5.1 Definitions

10.5.1.1 Definition of AE

AE Definition

- An AE is any untoward medical occurrence in a participant, temporally associated with the use of study intervention, whether or not considered related to the study intervention.
- NOTE: An AE can therefore be any unfavorable and unintended sign (including an abnormal laboratory finding), symptom, or disease (new or exacerbated) temporally associated with the use of a study intervention.

Events Meeting the AE Definition

- Any abnormality or deterioration in a laboratory test results (hematology, clinical chemistry, or urinalysis) or other safety assessments (eg, ECG, radiological scans, vital signs measurements), including those that worsen from baseline, or are considered clinically significant in the medical and scientific judgment of the Investigator.
- Exacerbation of a chronic or intermittent pre-existing condition including either an increase in frequency and/or intensity of the condition.
- A new condition detected or diagnosed after study intervention administration even though it may have been present before the start of the study.
- Signs, symptoms, or the clinical sequelae of a suspected drug-drug interaction.
- Signs, symptoms, or the clinical sequelae of a suspected overdose of either study intervention or a concomitant medication.
- Serious events that are related to a protocol-mandated intervention, including those that occur prior to assignment of study procedures (eg, screening invasive procedures, such as biopsies, discontinuation of non-study medications that may be required by protocol such as a prohibited medication).
- Any new cancer (that is not a condition of the study).
- Note: Progression of the cancer under study is not a reportable event. Refer to [Section 8.3.6](#) for additional details.

Events NOT Meeting the AE Definition

- Medical or surgical procedure (eg, endoscopy, appendectomy): the condition that leads to the procedure is the AE.
- Situations in which an untoward medical occurrence did not occur (social and/or convenience admission to a hospital).
- Anticipated day-to-day fluctuations of pre-existing disease(s) or condition(s) present or detected at the start of the study that do not worsen.
- Surgery planned prior to informed consent to treat a pre-existing condition that has not worsened.

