10.5.1.4 Definition of Treatment-emergent AE

Treatment-emergent AE Definition

- Any unfavorable and unintended diagnosis, symptom, sign (including an abnormal laboratory finding that is considered to be clinically significant), syndrome or disease that either occurs during the study, having been absent at baseline, or, if present at baseline, appears to have worsened in severity or frequency, whether or not the event is considered related to the study intervention.

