- If a persistent AE becomes more severe, the most extreme severity should also be recorded on the Adverse Event eCRF page, and details regarding any increases or decreases in severity will be captured on the Adverse Event eCRF.
- If the event becomes serious, it should be reported to the Sponsor as a SAE, and the Adverse Event eCRF page should be updated by changing the event from “non-serious” to “serious,” providing the date that the event became serious, and completing all data fields related to SAEs.
- A recurrent AE is one that resolves between participant evaluation time points and subsequently recurs. Each recurrence of an AE should be recorded as a separate event on the Adverse Event eCRF page.

Abnormal Laboratory Values

- A clinical laboratory test value must be reported as an AE if it meets any of the following criteria:
 - is accompanied by clinical symptoms
 - results in a change in study intervention (eg, dose modification, treatment interruption, or treatment discontinuation)
 - results in a medical intervention or change in concomitant medication
 - is clinically significant in the Investigator’s judgment

Abnormal Vital Sign Values

- Medical and scientific judgment should be exercised in deciding whether an isolated vital sign abnormality should be classified as an AE.
- If a clinically significant vital sign abnormality is a sign of a disease or syndrome (eg, high blood pressure), only the diagnosis (ie, hypertension) should be recorded on the Adverse Event eCRF page.
- Observations of the same clinically significant vital sign abnormality from visit to visit should only be recorded once on the Adverse Event eCRF page (see above for details on recording persistent AE).

Abnormal Liver Function Tests

- The finding of an elevated alanine aminotransferase (ALT) or aspartate aminotransferase (AST) ($> 3 \times$ baseline value) in combination with either an elevated total bilirubin ($> 2 \times$ upper limit of normal [ULN]) or clinical jaundice in the absence of cholestasis or other causes of hyperbilirubinemia is considered to be an indicator of severe liver injury (as defined by Hy's Law). Therefore, Investigators must report as an AE the occurrence of either of the following:
 - Treatment-emergent ALT or AST $> 3 \times$ baseline value in combination with total bilirubin $> 2 \times$ ULN (of which $\geq 35\%$ is direct bilirubin)
 - Treatment-emergent ALT or AST $> 3 \times$ baseline value in combination with clinical jaundice

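### Protocol 8.2.5 words clinical significance so that worse-than-expected laboratory findings drop out, and four passages set unreconciled thresholds for counting a laboratory abnormality as an AE

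*Protocol*

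**What the plan says.** The sole primary endpoint is "Incidence and severity of AEs" (Protocol 3). Five passages bear on whether a laboratory abnormality enters it.

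- **Protocol 8.2.5.** The Investigator must label each laboratory result as clinically significant or not. The first limb is "Clinically significant abnormal findings are those for which an action was taken". The second is "or those that are not associated with the underlying disease, unless judged by the Investigator to be more severe than expected", with expectation measured against the participant's own condition. The stated consequence is "Clinically significant changes occurring during the study should be documented on the appropriate eCRF". The section does not itself mention AEs.
- **Protocol 10.5.1.1.** The events that meet the AE definition include "Any abnormality or deterioration in a laboratory test results (hematology, clinical chemistry, or urinalysis" and other safety assessments. Clinical significance appears only as an alternative: "or are considered clinically significant in the medical and scientific judgment of the Investigator".
- **Protocol 10.5.5.** "A clinical laboratory test value must be reported as an AE if it meets any of the following criteria". The criteria are accompanying symptoms, a change in study intervention, a medical intervention or change in concomitant medication, and clinical significance in the Investigator's judgment.
- **Protocol 10.5.1.4.** For treatment-emergent AEs, the laboratory case is "an abnormal laboratory finding that is considered to be clinically significant". Protocol 9.3.2 uses this definition for the incidence summaries.
- **SAP 5.5.2.** A treatment-emergent AE is any event that is new or worse after treatment starts. There is no clinical-significance qualifier for laboratory findings, and the list of differences in SAP 6 does not mention its removal.

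SAP 5.5.3 plans descriptive statistics for laboratory data and optional changes from baseline. It does not specify a graded table.

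**The concern.** There are two faults, and they compound each other.

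The first is in the 8.2.5 sentence. Its *unless* clause is attached to findings that are not associated with the disease. As written, a finding unrelated to the disease stops being clinically significant when it is judged worse than expected, and a disease-associated finding is never significant without an action, however far it exceeds expectation. The clause makes sense only as an exception for disease-associated findings.

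The second is that no passage says which threshold governs. Protocol 8.3 sends sites to Appendix 5 for the definition and has them collect all AEs. Within that appendix, 10.5.1.1 is broad, while 10.5.5 and 10.5.1.4 are narrower. If 10.5.1.1 governs, the four criteria in 10.5.5 are redundant. If 10.5.5 is meant to govern, 10.5.1.1 is too wide.

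Two sites seeing the same asymptomatic value could therefore record it differently while each follows the protocol. In a cohort of 15, a few discretionary entries visibly move an incidence.

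**Working it through.** **1. The plan's own figures.** Exact 95% limits for x events in n participants are the 2.5% quantile of Beta(x, n−x+1) and the 97.5% quantile of Beta(x+1, n−x). All 12 intervals in Protocol Table 5 (SAP Table 2) reproduce to one decimal. For example, 2/15 gives 1.7% to 40.5%, and 12/30 gives 22.7% to 59.4%.

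For the two-stage rule (at least 2/15, then at least 6/30):

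- P(X ≤ 1 | n = 15, p = 0.10) = 0.549 (stated 55%).
- The rejection probability is the sum over x = 2 to 15 of P(X = x)·P(Y ≥ 6−x), with X and Y both Bin(15, p). It is 0.0684 at p = 0.10 (stated 0.07) and 0.7745 at p = 0.25 (stated 77%).

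The posterior for 6/15 is Beta(0.5+6, 2.5+9) = Beta(6.5, 11.5), and P(rate > 0.30) = 0.692 (stated 0.69). None of these uses the definition of a laboratory AE, so none changes.

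**2. The 8.2.5 sentence, case by case.** The sensible reading makes disease-associated findings non-significant unless worse than expected.

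| Finding | Literal 8.2.5 | Sensible reading |
|---|---|---|
| Action taken | significant | significant |
| Unrelated to disease, not worse than expected, no action | significant | significant |
| Unrelated to disease, worse than expected, no action | **not significant** | significant |
| Disease-associated, as expected, no action | not significant | not significant |
| Disease-associated, worse than expected, no action | **not significant** | significant |

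The readings differ in the third and fifth rows. In both, the finding was judged worse than expected and no action was taken.

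**3. The thresholds side by side.** Take a new abnormality with no symptoms, no action and no judgment of clinical significance.

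| Passage | Does it count? |
|---|---|
| Protocol 10.5.1.1 | Yes, as an abnormality or deterioration |
| Protocol 10.5.5 | Reporting not required |
| Protocol 10.5.1.4 | Does not qualify as treatment-emergent through the laboratory wording |
| SAP 5.5.2 | Yes, if it was reported as an AE |

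If the value is symptomatic or acted on, 10.5.5 makes reporting mandatory and the passages largely agree. The divergence is therefore confined mainly to asymptomatic values on which nobody acted.

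**4. Illustration of size.** The documents give no rate of laboratory abnormalities, so every share here is an assumption. Let x of 15 have a given laboratory AE under the narrower criteria, and let a share q of the remaining 15−x qualify only under 10.5.1.1. The new count is x + q(15−x), rounded to a whole participant.

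| x | q | New count | Incidence | Exact 95% CI |
|---|---|---|---|---|
| 2 | 0 | 2 | 13.3% | 1.7 to 40.5% |
| 2 | 0.25 | 2 + 3.25 → 5 | 33.3% | 11.8 to 61.6% |
| 2 | 0.50 | 2 + 6.5 → 9 | 60.0% | 32.3 to 83.7% |
| 2 | 1 | 15 | 100% | 78.2 to 100% |
| 4 | 0 | 4 | 26.7% | 7.8 to 55.1% |
| 4 | 0.25 | 4 + 2.75 → 7 | 46.7% | 21.3 to 73.4% |
| 4 | 0.50 | 4 + 5.5 → 10 | 66.7% | 38.4 to 88.2% |
| 4 | 1 | 15 | 100% | 78.2 to 100% |

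The choice of passage can matter. The table does not estimate how much it does.

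**The case against.** The best defence is that 8.2.5 is not the AE rule. It governs a designation on the laboratory report, it does not mention AEs, and 10.5.5 relies on the Investigator's judgment without citing it. That stands. The link from 8.2.5 to the endpoint runs only through the shared term in 10.5.5 and 10.5.1.4, and an Investigator can report a worse-than-expected value on judgment alone. Section 10.5.5 also has worsening pre-existing conditions recorded as AEs and directs that doubtful cases of disease progression be reported. Much of what the literal 8.2.5 text omits can therefore still reach the AE record.

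Several stronger readings are tempting, and the documents do not support them:

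- *That 10.5.1.1 and 10.5.5 contradict each other.* Section 10.5.5 says when a value must be reported, not that no other value may be. The parent AE definition also asks for something untoward or unfavorable. This is an unreconciled difference in threshold, not a logical contradiction.
- *That laboratory AE incidence would approach 100%.* Table 4 lists about 26 quantitative analytes (10 hematology, 16 chemistry). With an independent 5% chance each of lying out of range, 1 − 0.95^26 = 0.74 for at least one at a single draw; with 1%, 1 − 0.99^26 = 0.23. Independence is implausible for red cell count, hemoglobin and hematocrit, or for ALT and AST. Baseline abnormalities that do not worsen are not treatment-emergent. Table 5 concerns one specific AE, not any analyte.
- *That safety oversight fails in the same way.* The Safety Assessment Committee reviews laboratory data as well as AEs (Protocol 9.5.1, SAP 4.3). Its 4/15, 8/30 and ≥ 6 triggers use toxicity criteria set in cohort appendices that are not among these documents.
- *That cohort comparisons are spoiled.* The SAP disclaims comparison between cohorts. The issue is consistency across sites within a cohort.

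What the defence does not answer is that no passage states which threshold governs. The separate laboratory summaries do not fill the gap, because no table by grade is specified.

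**Conclusion.** The point holds in a limited form. The 8.2.5 sentence is defective as written, and Protocol 10.5.1.1, 10.5.1.4, 10.5.5 and SAP 5.5.2 do not apply one threshold. The consequence is confined mainly to asymptomatic laboratory abnormalities with no action taken. Those still feed the only primary endpoint, so their incidence can depend on which passage a site follows.

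The actual size cannot be determined from the documents, because it depends on how often such abnormalities occur and on how sites were trained. The move from 13.3% to 33.3% rests on an assumed share of one quarter and shows only how sensitive a cohort of 15 is. The plan's stated statistical figures stand. This should be corrected, but it does not undermine the design.

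**What to change.** 1. **Protocol 8.2.5.** Reword the sentence so that the exception attaches to disease-associated findings: these are not clinically significant unless judged worse than expected. State separately how findings unrelated to the disease are to be classed.
2. **Protocol 10.5.1.1, 10.5.1.4, 10.5.5 and SAP 5.5.2.** Reconcile them to one stated rule, with cross-references. Which threshold to adopt is the sponsor's choice. If the SAP is meant to depart from 10.5.1.4, list that in SAP 6.
3. **SAP 5.5.3.** Add a table of treatment-emergent laboratory abnormalities by worst CTCAE v5.0 grade, derived from the recorded values where the CTCAE criteria are numeric. This gives a measure that does not depend on what sites chose to report, including for data already collected.

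The wording can go into the protocol amendment that SAP 6 already announces. The cost is one extra table from laboratory data already planned for collection, and a small discontinuity with AEs recorded under the old text, which the study report should note.

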8.2.5.1 Local Laboratory Assessments

Samples for the laboratory tests in [Table 4](#) will be sent to the study site's local laboratory for analysis:

Table 4: Laboratory Tests Sent to the Study Site’s Local Laboratory for Analysis of Safety

Profile	Laboratory Test
Hematology	RBC count hemoglobin hematocrit WBC count with automated differential (neutrophils, eosinophils, basophils, monocytes, lymphocytes, other cells) platelet count manual differential, if clinically indicated
Clinical Chemistry (Serum or Plasma)	sodium potassium chloride bicarbonate glucose BUN or urea creatinine total protein albumin calcium total bilirubin alkaline phosphatase ALT AST LDH TSH (T3 and FT4 should be checked if TSH is outside the normal range) coagulation assessments (PT, PTT, INR) ^a
Urinalysis	

ALT = alanine aminotransferase; AST = aspartate aminotransferase; BUN = blood urea nitrogen; INR = international normalized ratio; LDH = lactate dehydrogenase; PT = prothrombin time; PTT = partial thromboplastin time; RBC = red blood cell; TSH = thyroid stimulating hormone; WBC = white blood cell

^a Coagulation assessment not required during treatment phase unless indicated

